10.1 Handling and storage of data and documents	
10.2 Amendments	
10.3 End of study report	
10.4 Public disclosure and publication policy	
11. REFERENCES	21
12. APPENDIX	25

LIST OF ABBREVIATIONS AND RELEVANT DEFINITIONS

TVU	Trans Vaginal Ultrasonography
SIS	Saline Infused Sonography
GIS	Gel Infused Sonography
CS	Caesarean Section
SD	Standard Deviation
IUD	Intra Uterine Device
LUS	Lower uterine segment
FSFI	Female Sexual Function Index
SF36	Short Form healthy questionnaire
EuroQOL	Generic Quality Of Life
VAS	Visual Analogue Score

SUMMARY

Rationale: A niche is a defect that can develop at the site a caesarean section scar. A niche can cause complaints of abnormal uterine blood loss, dysmenorrhea, chronic pelvic pain and is related to infertility. Several innovative surgical therapies have been developed to treat niche related symptoms. A laparoscopic resection of the niche is preferred in a large (residual myometrium $\leq 3\text{mm}$) symptomatic niche. Reduction of symptoms and promising reproductive outcomes at a low complication rate have been reported in a few case series and cohort studies.

Hypothesis: A laparoscopic niche resection will lead to better reproductive outcomes than expectant management in patients with secondary unexplained subfertility and a large niche.

Objectives: The aim of the study is to evaluate the effect of a laparoscopic niche resection in patients with secondary unexplained subfertility or failed IVF in comparison to expectant management on fertility, pregnancy outcome and postmenstrual spotting. Cost-effectiveness analysis will be executed alongside the study.

Intervention: Laparoscopic niche resection, contraceptives during the first 6 months to enable healing of the uterine scar before a pregnancy is allowed, thereafter fertility therapies are allowed if needed, according to the local protocol.

Control: Expectant management for 12 months without contraceptives, fertility therapies are allowed if needed, laparoscopic niche resection is allowed after 12 months according to the local protocol.

Setting: The study will be executed in centres with sufficient experience in executing laparoscopic niche resections (> 30 previous laparoscopic niche resections). Randomisation will be performed centrally, webbased, stratified per recruiting centre using permuted block design of 2 and 4. Randomisation ratio for intervention versus control group will be 1:1.

Study population: Women (>18 years) with the presence of a large niche and secondary unexplained subfertility, failed IVF, or with problems during their fertility therapy, such as intrauterine accumulation of fluid and/ or difficulties during the introduction of the ET of IU catheter will be included.

Main study outcomes: *Primary outcome:* time to ongoing pregnancy, defined as a intrauterine pregnancy with a fetal heartrate at 12 weeks gestation. *Secondary outcomes:* Fertility and pregnancy outcomes, satisfaction and quality of life, surgical outcomes (intervention group), additional interventions, niche characteristics.

Economic evaluation: direct and indirect costs will be executed from a social perspective.

Measurements: will be performed at baseline, 3, 6, 12 and 24 months after randomisation (control) or surgery (intervention) using digital questionnaires. Niche features will be measured by sonohysterography (SIS/GIS) at baseline and at 3 months after randomisation (control group) or after surgery (intervention group) . Patients are motivated for measurement of the lower uterine segment (LUS) at 12, 20 weeks and at 30 weeks of gestation during regular pregnancy check-ups. Prognostic dissimilarities will be registered, like duration of subfertility and previous therapies. Medical consumption and medication use will be registered in a diary.

Sample size calculation: Assuming 40% pregnancies in the intervention group, 20% pregnancies in the control group, a significance level of 0.05 and a power of 0.80, we need 82 women in each group. Because we expect a drop-out rate of about 15%, we will include 100 subjects in each group. Primary outcome is time to an ongoing pregnancy.

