6.2 Randomisation, blinding and treatment allocation

The patients will be asked by their gynaecologist (at the local centre) to participate in the trial. Patients will be randomly allocated to laparoscopic niche resection or expectant management for 12 months. Eligible patients will be informed about the aims, methods, design, benefits and possible disadvantages of the laparoscopic niche resection due to informed consent. The patient will be included in the study after signing informed consent. Then the randomisation will be performed centrally using a permuted block-design, stratified for recruiting centre.

Given the nature of the therapy, blinding is not possible.

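### Small centre-level blocks of 2 and 4, printed in the protocol of an open trial, let recruiters partly predict the next allocation and so weaken concealment

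*Protocol*

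**What the plan says.** The Summary, under Setting, gives the mechanism and the ratio: "Randomisation will be performed centrally, webbased", "stratified per recruiting centre using permuted block design of 2 and 4", and "Randomisation ratio for intervention versus control group will be 1:1". Sections 3 and 6.2 repeat the central permuted-block design with centre as the only stratum, but without the sizes.

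Section 6.2 also says "Given the nature of the therapy, blinding is not possible" and "The patients will be asked by their gynaecologist (at the local centre) to participate in the trial". Section 8.2 adds that the supervising gynaecologist or the attending resident informs the patient, and that consent is signed before randomisation.

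The protocol does not say whether the two block sizes follow each other at random, and it does not say that they are withheld from recruiting staff.

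**The concern.** In a permuted block the arms must balance by the end of the block, so past allocations carry information about the next one. The information is greatest when blocks are short, when their sizes are known, when each stratum is one centre whose staff can see what happened to earlier women, and when treatment is open. All four conditions can apply here; surgery or no surgery is plain to local staff.

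A recruiter who thinks the next arm is likely to be surgery, or likely to be expectant management, can bring forward, delay or omit an invitation according to a woman's prognosis. Age, duration of subfertility and earlier IVF failure are known before she is approached, and they bear on the primary outcome, time to ongoing pregnancy. Selection of this kind would make the arms differ at baseline, and adjustment reaches only the factors that are recorded.

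**Working it through.** The protocol states no figure on predictability, so there is none to reproduce.

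**Inputs from the protocol.** Block sizes 2 and 4, ratio 1:1, centre as the only stratum (Summary, Setting; section 6.2). No blinding, local recruiters (section 6.2). Planned size 130 (section 4.3) or 200, as 100 per group (Summary; section 7).

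**Assumptions, not in the protocol.** The two sizes are drawn at random with equal probability (mixes of 2:1 and 1:2 also tried). There are 20 women per centre (10 and 40 also tried). The share of earlier arms that the recruiter sees is 100% at the upper end, with lower shares tried.

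**Simple cases by hand.**
- Blocks of 2 only: the first allocation is a coin toss and the second is certain. Correct guesses are (0.5 + 1)/2 = 75%; certain allocations are 1/2 = 50%.
- Blocks of 4 only: the chances of a correct guess at positions 1 to 4 are 1/2, 2/3, 2/3 and 1. Their mean is 2.833/4 = 70.8%. Position 3 is certain with probability 1/3 and position 4 always, so certain allocations are (1/3 + 1)/4 = 33%.
- Equal mix of 2 and 4, second woman at a centre: the block is of size 2 with probability 1/2 (opposite arm certain) or of size 4 with probability 1/2 (opposite arm 2/3). The opposite arm follows with probability 0.5 × 1 + 0.5 × 2/3 = 5/6, or 83%.
- If the first two women at a centre receive the same arm (probability 1/2 × 1/3 = 1/6), the block must be of size 4, and the third and fourth allocations are both certain.

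**Whole sequence.** An observer who knows the possible sizes but not the block boundaries updates the probability of the next arm by Bayes' rule after each allocation seen. The simulation used 8,000 sequences per setting. Results for full observation:

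| Block sizes | Women per centre | Guessed correctly | Certain |
|---|---|---|---|
| 2, 4 (equal mix) | 10 | 71.3% | 9.5% |
| 2, 4 (equal mix) | 20 | 71.8% | 10.4% |
| 2, 4 (equal mix) | 40 | 72.0% | 10.8% |
| 2, 4 (mix 2:1 or 1:2) | 10 to 40 | 71% to 73% | 7% to 13% |
| 4, 6 | 20 | 68.5% | 5.7% |
| 4, 6, 8 | 20 | 67.2% | 2.3% |

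With blocks of 2 and 4, about 55% of allocations can be called with a probability of at least 75%.

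**Partial observation** (blocks 2 and 4, equal mix, 20 women per centre; the recruiter knows how many women were randomised but sees only some of the arms):

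| Earlier arms seen | Guessed correctly | Certain |
|---|---|---|
| 75% | 65.5% | 4.7% |
| 50% | about 60% | about 1.5% |
| 33% | 57.1% | 0.5% |

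**In women.** At about 10% certain, 0.10 × 130 = 13 and 0.10 × 200 = 20 allocations would be known in advance under full observation. At 1.5% these are 0.015 × 130 = 2 and 0.015 × 200 = 3. With blocks of 4, 6 and 8 under full observation, 0.023 × 130 = 3 and 0.023 × 200 = 4.6.

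**The case against.** The strongest objection concerns what a recruiter knows. A reader might infer that one gynaecologist per centre sees each earlier allocation and also invites the next woman, so that 10% certainty is a fact of the design. The documents do not support that. Sections 6.2 and 8.2 allow several gynaecologists and residents to recruit at one centre, and nothing says that any of them follows the ordered sequence of arms. This part stands: the full-observation figures are an upper bound, and they fall quickly as fewer arms are seen.

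A reader might also infer that concealment was in fact broken, or that the primary result is biased. Neither follows. The calculation measures guessability, not bias in time to pregnancy, and the protocol holds no evidence of selective enrolment.

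The plan also has safeguards. Randomisation is central and consent comes first. Section 8.2 intends that every eligible woman be informed. Section 3 registers the number of exclusions and the reasons for them. The Summary registers duration of subfertility and previous therapies. These help to detect selection or adjust for it, but they do not stop a recruiter from timing an invitation.

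Finally, small blocks keep the arms balanced in small centres, and larger blocks lower the guess rate only from about 72% to 67%. Both points are true. The larger gain is in certain allocations, from about 10% to about 2%, which is why concealing the sizes matters as well as enlarging them.

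**Conclusion.** The point holds as a weakening of allocation concealment, not as a demonstrated failure. The protocol fixes short blocks within single-centre strata and discloses their sizes in an open trial recruited locally; central web-based allocation does not remove the resulting predictability.

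Its size depends on unstated inputs: from about 72% correct and 10% certain when every earlier arm at the centre is seen, down to about 60% and 1.5% when half are seen. The certain share under full observation moves between 7% and 13% with the mix of the two sizes, and little with 10 to 40 women per centre. If the sizes followed a fixed order that staff could learn, predictability would be higher. The effect on the hazard ratio for ongoing pregnancy cannot be derived from the protocol. The change is worth making because it is cheap, not because harm has been shown.

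**What to change.** 1. Delete the block sizes from the protocol that sites hold, and keep them in a randomisation file with restricted access.
2. In section 6.2, state that block sizes vary at random and are concealed from all recruiting staff.
3. For allocations still to be made, use larger randomly varied blocks within centre, for example 4, 6 and 8.

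The cost is one setting in the web system and a short protocol change. The possible imbalance inside an unfinished block at a centre rises from 2 women (4/2) to 4 women (8/2), a modest loss of balance in a trial of 130 to 200. Sites that have already read the sizes cannot unlearn them, so step 1 alone would not protect those centres; step 3 is needed there.

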1. INTRODUCTION

In Western countries caesarean sections are rising. A niche is a cavity that develops at the site of a uterine caesarean section scar and is more frequently described over the last years (1-4). A niche can be visualised with sonohysterography and is defined as an indentation at the site of a caesarean scar with a depth of at least 2 mm (1-4). Previous studies have shown that approximately in 60% of the women who have undergone a CS a niche can be visualised. A niche can cause complaints of abnormal uterine blood loss, dysmenorrhea, chronic pelvic pain (1-4) and infertility (11;12).

A recent meta-analysis reported that a CS on average reduced the probability of subsequent pregnancy with 10% (RR 0.91; 95% 0.87-0.95) in comparison to a vaginal delivery. In a recent prospective cohort study including 101 patients (Vervoort et al. 2016, submitted) good results are reported after the laparoscopic niche resections and uterine repair. It can be hypothesized that niches may play a role in this. In theory a niche and related accumulation of blood, mucus and fluid in the niche and uterus may impair the penetration of sperm cells and the implantation of embryo's (7). Sometimes a niche in combination with a retroflexed uterus may hamper the insertion of an insemination or embryo transfer catheter due to distorted anatomy.

Several innovative surgical treatments have been developed to treat niche related symptoms (6;8;11-14). The least invasive surgical therapy is a hysteroscopic niche resection, which can be performed in day-care setting in small symptomatic niches (residual myometrium of $\geq 3\text{mm}$) (16). In case a niche is larger (residual myometrium of $\leq 3\text{mm}$) a laparoscopic resection (or vaginal resection) is preferred because of the risk to cause bladder injury during a hysteroscopic resection.

Based on a previous systematic review several niche therapies have been applied in patients with niche related gynaecological symptoms and in patients with a niche and subfertility. Promising results have been described on gynaecological and reproductive outcome. However most studies had a small sample size and did not have a comparative group (4). This review that was executed in 2014, included only one study (case series) reporting on laparoscopic niche resection to treat niche related spotting and conclude to relieve pain and spotting symptoms in all 13 patients (11). Since then, several case reports and case series had been published (included patients varied from 1 to 22) (11; 17-36). Tanimura et al. and Jeremy et al. described fertility after the intervention as a primary outcome, including 23 women with secondary subfertility after their last caesarean section. One year after the laparoscopic niche resection 56-71% of the women got pregnant (14;26). The residual

myometrial thickness was found to be increased after laparoscopic niche resection in all studies.

Recently a prospective cohort study has been executed in the VUmc including patients with a large niche and gynaecological symptoms. The majority of the patients had secondary subfertility (94.7%) or failed previous IVF therapy (42%). 42 of 99 patients had mid-cycle intrauterine fluid collection. So far 101 patients underwent a laparoscopic niche repair. The preliminary results are promising concerning the reduction of gynaecological symptoms and reproductive outcomes at a reported promising results with relatively low complication rate. In total 73% of the patients conceived within 3 months after they started with unprotected intercourse (72.2%) or assisted reproductive therapies (Vervoort et al. submitted). Controlled studies including laparoscopic niche repair are lacking.

In current practice we see many niches in particular in patients seeking help or undergoing assisted reproductive therapy because of secondary unexplained subfertility. While previous studies report promising results of laparoscopic niche resection concerning pregnancy outcomes, we do not know if these outcomes are better than after expectant management. This can only be studied properly in a randomised trial. The aim of the current study is to compare the effect of a laparoscopic niche resection compared to expectant management in women with secondary unexplained subfertility or failed IVF and a large niche with a residual myometrium less than 3mm on reproductive outcomes.

2. OBJECTIVES

Primary objective:

- To determine the effectiveness of a laparoscopic niche resection in women with a large niche and secondary unexplained subfertility or failed IVF therapies because of intra-uterine fluid accumulation on the time to achieve an ongoing pregnancy defined as an intra-uterine pregnancy of a fetus with a positive heart activity at 12 weeks gestation.

Secondary objectives:

- To assess reproductive outcome, pregnancy outcome, quality of life, postmenstrual spotting, menstrual pain, surgical and anatomical outcomes, applied interventions, medical consultations and costs.

3. STUDY DESIGN

Multicentre randomised controlled trial.

Patients with the presence of a large niche after CS and failed IVF or secondary unexplained subfertility or with problems during their fertility therapy, such as intrauterine accumulation of fluid and/ or difficulties during the introduction of the ET of IU catheter and not meeting any of the exclusion criteria are eligible to be randomised.

Patients will be randomly allocated to laparoscopic niche resection or expectant management for 12 months. Informed consent will be given. The patient will be included in the study after signing informed consent. Then the randomisation will be performed centrally using a permuted block-design, stratified for recruiting centre.

All patients excluded from the study will be registered in order to record the number and reason of exclusion.

4. STUDY POPULATION

4.1 Inclusion criteria

Women with the presence of a large niche* after CS and

1. Secondary unexplained subfertility

or

2. failed IVF

or

3. problems during fertility therapy, such as intrauterine accumulation of fluid and/ or difficulties during the introduction of the ET of IU catheter, and not meeting any of the exclusion criteria are eligible to be randomised.

* A large niche is defined as a niche with a depth of $> 50\%$ of the myometrial thickness and a residual myometrium $\leq 3\text{mm}$ in one of the ultrasound planes measured with GIS or SIS ultrasonography

4.2 Exclusion criteria

Pregnancy, age < 18 years, contraindications for general anaesthesia, a (suspected) malignancy, uterine or cervical polyps, submucosal fibroids, atypical endometrial cells, cervical dysplasia, cervical or pelvic infection, hydrosalpinx.

4.3 Sample size calculation

Assuming a HR of 1.8, an alpha of 0.05 and a drop-out ratio of 20% we intend to include 130 patients in order to achieve a power of 80%.

5. TREATMENT OF SUBJECTS

Investigational product/treatment

In this trial outcomes of laparoscopic niche resection will be compared to expective management (usual care).

Intervention group

In the therapy group fertility therapies will be allowed from 6 month onwards after laparoscopic niche resection, the uterine scar needs to heal before a pregnancy is allowed.

The patients allocated for laparoscopic niche resection will undergo a planned procedure under general anaesthesia in lithotomic position. Donnez et al. first describe the laparoscopic niche resection in 2008 (19). The niche resection is continuously guided by hysteroscopy. Strong adhesions are often seen between the niche/uterus and the bladder or the niche/uterus and the abdominal wall. Adhesions are lysed and the bladder is dissected from the anterior wall of the uterus and the niche. Due to the thin myometrium at the site of the niche, the niche can be illuminated with the hysteroscopic light and can be visualised laparoscopically. The niche and related fibrotic tissue is resected. The uterotomy is closed using at least four sliding knots that include the entire uterine wall including the endometrium. One inverted suture is placed across the closed wound to strengthen the wound. In case the uterus is (extreme) retroverse flexed, the round ligaments are shortened using 2 continuous running sutures (2.0 multifilament) (38). The anatomic result of niche closure is evaluated by hysteroscopy at the end of the procedure.

Control group/ expectant group

The control group will not receive any additional surgical intervention during the first twelve months. Patients are allowed to conceive immediately and if needed fertility therapies are allowed, indication for the fertility therapy will be based on the local protocol.

6. METHODS

6.1 Study parameters/ outcome

6.1.1 Primary outcome:

Time to ongoing pregnancy, defined as a intrauterine pregnancy with a fetal heartrate at 12 weeks gestation.

6.1.2 Secondary outcomes:

Fertility and pregnancy outcomes:

- time to conceive
- number of (vital) pregnancies
- number of take home babies
- number of miscarriages
- number of patients with term delivery
- complications during pregnancy
- mode of delivery
- complications during the delivery

Satisfaction and QOL

- satisfaction (Lickert scale)
- Quality of life (SF36)
- EuroQol SD5

Gynecological symptoms:

- pain during menstruation (VRS)
- abdominal pain on non-menstruating days (VRS)
- urinary symptoms (shortlist of SFFI)
- reduction of postmenstrual spotting days

Surgical outcomes (intervention group):

- surgery time
- blood loss during surgery
- perioperative complications (major and minor).

Additional interventions:

- hormonal interventions to treat gynecological symptoms

- additional surgical interventions
- applied fertility therapies.

Niche characteristics:

- immediately after surgery using hysteroscopy

Niche characteristics 3 months after randomization:

- residual niche (size, volume)
- residual myometrium (RM)
- intra-uterine fluid collection
- angle between endometrial lining of the endocervix and corpus
- residual myometrium or thickness LUS during subsequent pregnancy (at 12, 20 and 30 weeks).

6.1.3 Other study parameters:

Baseline parameters: age, body mass index, ethnic background, religion, gestational age, previous vaginal delivery, maternal disease, planned or emergency section, cervical dilatation, birth weight, placental localisation, multiple pregnancy and postpartum complications (infection, hospital readmission) will be registered.

6.2 Randomisation, blinding and treatment allocation

The patients will be asked by their gynaecologist (at the local centre) to participate in the trial. Patients will be randomly allocated to laparoscopic niche resection or expectant management for 12 months. Eligible patients will be informed about the aims, methods, design, benefits and possible disadvantages of the laparoscopic niche resection due to informed consent. The patient will be included in the study after signing informed consent. Then the randomisation will be performed centrally using a permuted block-design, stratified for recruiting centre.

Given the nature of the therapy, blinding is not possible.

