6.3.1 Methods and measurements

Before randomisation, in every patient a transvaginal ultrasound (TVU) and a saline infusion sonography (SIS) or gel infusion sonography (GIS) is performed to assess the niche. Both procedures are subject of normal diagnostic tools for defining the origin of their gynaecological complaints. During ultrasound (SIS or GIS) the niche will be measured in the sagittal plane where the largest niche is visible (maximum depth, thinnest residual myometrium). Depth, width, largest diameter, residual myometrium and the shape of the main niche will be registered in the sagittal and transversal plane. In case of a lateral branch of the niche depth, width and the residual myometrium of the branch will be additionally registered. (see appendix A, figure numbers 1-4) Besides measurements of the niche, other features such as position of the uterus, vascular pattern and eventual fibroids or adenomyosis, intracavitary and/or niche fluid accumulations, abnormalities at the fallopian tubes and/or ovaries are registered.

For inclusion in the study the main niche needs to have a depth of > 50% of the total myometrium thickness at the anterior wall and a residual myometrium of less than 3mm in one of the ultrasound planes using sonohysterography.

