6.3.4 Niche evaluation during subsequent pregnancies

In both groups, a TVU will be repeated after 3 months. Patients willing to conceive will be followed to evaluate the course of their eventual pregnancy and its outcome. During their pregnancy ultrasounds at 12, 20 and 30 weeks will be made during regular check-ups evaluate the appearance and thickness of the residual myometrium. In order to standardize measurements, an e-learning program needs to be completed by the sonographers before participation to the study.

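### The ruling-out of blinding fits women and surgeons but not whoever makes the 3-month niche measurements, which are operator-dependent secondary outcomes with no masking stated

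*Protocol*

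**What the plan says.** Section 6.2 of the protocol deals with blinding in one sentence: "Given the nature of the therapy, blinding is not possible". It does not separate the woman, the surgeon and the person who assesses outcomes.

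Section 6.1.2 has a group of secondary outcomes under "Niche characteristics 3 months after randomization". It contains residual niche size and volume, residual myometrium, intra-uterine fluid and the angle between the linings of endocervix and corpus. Section 2 names anatomical outcomes among the secondary objectives.

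On how the niche is measured, section 6.3.1 says that "the niche will be measured in the sagittal plane where the largest niche is visible (maximum depth, thinnest residual myometrium"). On who measures it, section 6.3.4 says: "In order to standardize measurements, an e-learning program needs to be completed by the sonographers before participation to the study". Nothing in the protocol says what these sonographers may know about the allocation, or whether they may have taken part in the operation.

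**The concern.** An operation cannot be hidden from the woman who has it or from the surgeon who does it. Whether the sonographer knows of it is a separate question, and section 6.2 answers it with a reason that does not apply to that person. A plan followed as written would make no attempt to keep the allocation from the person taking the measurements.

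At stake is the anatomical comparison. The trial's rationale is that an uncorrected niche impairs fertility and that resection corrects it. Someone who knows that a repair was done may, without intending it, settle on a more favourable plane or read a small remnant more leniently. This would act in favour of the operated arm and make the anatomical effect look larger than it is.

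**Working it through.** No arithmetic settles this point, and the protocol has no figure of its own to reproduce. The check sets the relevant sections side by side.

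1. **Whom the reason covers.** The treatment is a laparoscopic resection under general anaesthesia (section 5), compared with no operation in the first twelve months. That rules out masking the woman and the surgeon. It does not by itself rule out masking a third person who scans the uterus months later.

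2. **When allocation can influence the reading.** Section 6.3.1 places the baseline scan before randomisation, so knowledge of the arm cannot affect it. The 3-month scan comes after. Any influence therefore falls on follow-up only, and adjustment for baseline would not remove it.

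3. **Whether the reading leaves room for judgement.** The operator must find the plane with the largest niche and the thinnest remaining muscle, on a scale where the inclusion cut-off for residual myometrium is 3 mm. That rule is written for the scan before randomisation. The Summary, however, plans sonohysterographic niche measurement at both time points, and no other measuring rule is given for 3 months.

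4. **What protects the reading.** The e-learning requirement in section 6.3.4 is the only safeguard. It makes technique more uniform between sonographers. It does nothing about a difference between arms that comes from knowing the arm.

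5. **Whether another outcome could replace this one.** Section 6.1.2 lists two other anatomical assessments. Hysteroscopy immediately after surgery exists only in the operated arm. Thickness of the lower uterine segment at 12, 20 and 30 weeks exists only in women who conceive. The 3-month scan is therefore the only planned post-treatment anatomical comparison of both arms in all women.

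6. **Size.** If the true difference between arms is D and knowledge of the arm shifts the readings by b, the expected observed difference is D + b. The protocol gives no D, no standard deviation and no reader error for any niche measure, so b cannot be derived. Only its likely direction can be stated: section 1 reports that residual myometrium increased after resection in all earlier studies, so an informed reader would expect an increase, and b would tend to have the same sign as D.

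A neighbouring inconsistency bears on the same outcomes. The Summary says "Niche features will be measured by sonohysterography (SIS/GIS) at baseline and at 3 months after randomisation (control group) or after surgery (intervention group"), whereas section 6.3.4 says "In both groups, a TVU will be repeated after 3 months" and section 6.1.2 counts the 3 months from randomisation without distinguishing the arms. Scan method and starting point must be reconciled for the outcome to be defined.

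**The case against.** The strongest objection is that masking would often fail. Section 5 describes removal of the niche, suturing through the full uterine wall and, in some women, shortening of the round ligaments. Scar appearance and uterine position may show the arm to anyone who scans. The woman may mention her operation. The Summary also puts operated women on contraceptives for the first 6 months and controls on none, so a question about contraception would disclose the arm. This stands: masking can reduce the bias but not remove it.

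The measuring rule and the 2 mm depth in the definition of a niche (section 1) also limit how far a reader can stray. They narrow the room for judgement without closing it.

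It may be said that such detail belongs in a statistical analysis plan. Who measures and what that person knows is a matter of trial conduct, and section 6.2 has already settled it.

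A reader might infer four stronger things that the protocol does not support:

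- **That masking needs no additional staff.** Section 6.3.4 mentions trained sonographers but not how many each centre has or who scans whom.
- **That surgeons will measure their own repairs.** The protocol does not exclude this, but does not plan it either.
- **That this scan is the sole direct evidence of anatomical correction.** The hysteroscopic and pregnancy measurements also exist, with the limits shown above.
- **That a specific inflation of the false-positive rate follows.** Any such figure would need an invented reading shift and would assume no true anatomical effect, contrary to what section 1 leads one to expect.

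**Conclusion.** The point holds in a limited form. The sentence in section 6.2 is justified for women and surgeons but too broad for the person who makes the 3-month niche measurements. Those measurements are operator-dependent secondary outcomes with no masking stated, and knowledge of the arm could exaggerate the difference between arms.

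The size of the bias is unknown and cannot be obtained from the protocol. The conclusion assumes that the 3-month scan is measured in the manner of section 6.3.1, and that at least some sonographers could be kept unaware of the arm in at least some women.

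The primary outcome, a pregnancy with a fetal heartbeat at 12 weeks, is little exposed to this kind of reading bias. The point is a cheap improvement of low weight and does not threaten the trial's main conclusion.

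**What to change.** Limit the sentence in section 6.2 to women and surgeons, and add a rule such as:

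> Where feasible, the 3-month niche measurements in both arms are made by an e-learning-trained sonographer who did not take part in the operation and is not told the allocation. The sonographer records whether the allocation became known. Measurements made without masking are reported as unmasked.

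In the same edit, reconcile the scan method and the start of the 3-month interval across the Summary and sections 6.1.2 and 6.3.4.

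The cost is protocol wording, one item on the case report form and some scheduling effort. No scan or visit is added, and the rule draws on sonographers already planned. A centre that cannot arrange this reports its readings as unmasked, which is why the rule says where feasible. The change must be in place before the 3-month scans it is meant to cover.
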